**Table 8-3. Statistical Comparisons for Pharmacokinetic Analysis of Normal and Impaired Renal Function**

Renal Function Categorization	Parameter	Comparison	
		Test Group	Reference Group
Creatinine Clearance (rounding to the nearest integer)	AUC inf , AUC last , C max	Mild Impairment CLcr 60-89 mL/min	Normal CLcr ≥ 90 mL/min
	AUC inf , AUC last , C max	Moderate Impairment CLcr 30-59 mL/min	Normal CLcr ≥ 90 mL/min
	AUC inf , AUC last , C max	Severe Impairment CLcr 15-29 mL/min	Normal CLcr ≥ 90 mL/min
MDRD-based eGFR (rounding to the nearest integer)	AUC inf , AUC last , C max	Mild Impairment eGFR 60-89 mL/min/1.73m 	Normal eGFR ≥ 90 mL/min/1.73m 
	AUC inf , AUC last , C max	Moderate Impairment eGFR 30-59 mL/min/1.73m 	Normal eGFR ≥ 90 mL/min/1.73m 
	AUC inf , AUC last , C max	Severe Impairment eGFR 15-29 mL/min/1.73m 	Normal eGFR ≥ 90 mL/min/1.73m 
	AUC inf , AUC last , C max	End Stage Impairment eGFR ≤ 14 mL/min/1.73m 	Normal eGFR ≥ 90 mL/min/1.73m 

For each PK parameter in comparison, a parametric (normal theory) analysis of variance (ANOVA) model will be fitted to the natural log-transformed values of PK parameter under evaluation. The statistical model will include renal function group as a fixed effect.

The following SAS PROC MIXED code will provide the group comparison analysis between the renal function groups and the 90% CI calculations for natural log-transformed PK parameters.

```
proc mixed;
  class renalgrp subjid;
  model lnest = renalgrp / ddfm=kr;
  repeated / group = renalgrp;
  lsmeans renalgrp / e diff cl alpha = 0.1;
  estimate 'Impaired versus Normal' treat 1 -1 / cl alpha = 0.10;
  ods output Estimates = LS_Diffs LSMeans = LS_Means CovParms = MSE;
run;
```

The ESTIMATE statement will be used to produce the point estimate and the corresponding 90% CI of the difference in PK parameters of interest on a logarithmic scale. The test-to-reference ratio (GLSM ratio) and associated 90% CI will be calculated by taking the exponential of the point estimate and the corresponding lower and upper limits, which is consistent with the two 1-sided tests approach {U.S. Department of Health and Human Services Food and Drug Administration Center for Drug Evaluation and Research (CDER) 2001, U.S. Department of Health and Human Services Food and Drug Administration Center for Drug Evaluation and Research (CDER) 2003}.

Nonparametric analyses for the PK parameters CL/F, Vz/F, and  $t_{1/2}$ , are routinely performed. When needed, these analyses can be performed using the Wilcoxon rank sum test for parallel design between the test and reference groups for GS-9876.

The following SAS PROC NPARLWAY code will provide the comparison.

```
proc nparlway data = param wilcoxon;  
  class treat;  
  var result;  
run;
```

To evaluate the protein binding of GS-9876, the percent of unbound GS-9876 at  $T_{max}$  and a later time point will be summarized by time point and renal function group. Protein binding data for individual subject will be presented in a listing.

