### 1.3. Study Design

Study GS-US-379-1932 is an open-label, parallel-group, adaptive, single-dose, multi-center Phase 1 study to evaluate the PK of GS-9876 in subjects with impaired renal function.

This study will target enrolling 20 to 60 subjects using an adaptive design that includes up to 3 enrolled cohorts of subjects with renal impairment and matched healthy controls. Based on safety and PK results from subjects with moderate renal impairment (Cohort 1), subjects with severe renal impairment (Cohort 2) and/or mild renal impairment (Cohort 3) will be enrolled as follows:

[figure not shown]
- Cohort 1 (Moderate Renal Impairment): Up to 20 subjects (10 per group, moderate renal impairment and matched healthy controls) for 8 evaluable subjects per group.
- Adaptive Cohort 2 (Severe Renal Impairment): Up to 20 subjects (10 subjects with severe renal impairment and up to 10 matched healthy control subjects if none of the healthy subjects from a previous cohort is an appropriate match for a severe impairment subject) for 8 evaluable subjects per group.

- Adaptive Cohort 3 (Mild Renal Impairment): Up to 20 subjects (10 subjects with mild renal impairment and up to 10 matched healthy control subjects if none of the healthy subjects from a previous cohort is an appropriate match for a mild impairment subject) for 8 evaluable subjects per group.

Adaptive Cohorts 2 and/or 3 will be enrolled as determined by safety and/or PK data in Cohort 1. Specifically, Cohort 2 (Severe Renal Impairment) will be evaluated if supported by safety and/or PK data from Cohort 1 (Moderate Renal Impairment). Cohort 3 (Mild Renal Impairment) will be evaluated if supported by safety and if substantial changes ( $\geq 2$ -fold mean difference from matched controls) in the exposure of GS-9876 is observed in subjects with moderate renal impairment in Cohort 1. Cohorts 2 and 3 may not be enrolled or may be enrolled sequentially or in parallel, as governed by safety and PK data in Cohort 1. Each control subject may be matched to multiple renal impaired subjects across different cohorts and can be matched to only 1 renal impaired subject within a cohort.

An overview of the study design is shown in [Figure 1-1](#).

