### **2.4. Changes from Protocol-Specified Analysis**

No changes from protocol-specified analyses are planned.

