#### **3.2. Strata and Covariates**

This study does not use a stratified randomization schedule in enrolled subjects. No covariates will be included in analyses.

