## 8.2. Statistical Analysis Methods

### 8.2.1. General considerations

Individual subject concentration data and individual subject PK parameters including percentage of protein binding for GS-9876 will be listed and summarized using descriptive statistics by renal function group. Summary statistics (numbers of subjects, mean, SD, coefficient of variation, median, minimum, maximum, Q1, and Q3) will be presented for both individual subject concentration data by time point and individual subject PK parameters by renal function group. Moreover, the geometric mean, 95% CI, and the mean and SD of the natural log-transformed values will be presented for individual subject PK parameter data.

Individual concentration data listings and summaries will include all subjects with concentration data. The sample size for each time point will be based on the number of subjects with nonmissing concentration data at that time point. The number of subjects with concentration BLQ will be presented for each time point. For summary statistics, BLQ values will be treated as zero at predose and one-half of the LLOQ for postdose time points.

Individual PK parameter data listings and summaries will include all subjects for whom PK parameter(s) can be derived. The sample size for each PK parameter will be based on the number of subjects with nonmissing data for that PK parameter.

In addition to the renal function categorization based on CLcr throughout this study, MDRD-based eGFR will be used for subject categorization in PK analysis. Subjects from all cohorts will be pooled and regrouped according to their MDRD-based eGFR values as follows:

- Normal renal function if eGFR (rounding to the nearest integer) is  $\geq 90$  mL/min/1.73m^2
- Mild impairment if eGFR (rounding to the nearest integer) is 60-89 mL/min/1.73m^2
- Moderate impairment if eGFR (rounding to the nearest integer) is 30-59 mL/min/1.73m^2

- Severe impairment if eGFR (rounding to the nearest integer) is 15-29 mL/min/1.73m^2
- End stage renal impairment if eGFR (rounding to the nearest integer) is  $\leq 14$  mL/min/1.73m^2

The following tables will be provided for GS-9876 by two sets of categorization (CLcr and MDRD-based eGFR) of renal function group:

- Individual subject concentration data and summary statistics
- Individual subject plasma PK parameters and summary statistics

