### **8.2.2. Statistical Methodology**

The statistical comparisons of the natural log-transformed PK parameters for GS-9876 between renal impaired subjects and healthy controls will be performed. All subjects with available data for the PK parameter under evaluation will be included in the modeling.

Consistent with using two sets of renal function categorization in PK summaries, two corresponding sets of comparisons will be performed. Details of these comparisons are shown in [Table 8-3](#). To ensure the appropriateness of applications of statistical testing, the comparisons will only be implemented when there are at least 3 subjects in both test and reference groups. The ratio of geometric least squares means (GLSMs) for the PK parameter in comparison between the test and reference groups and the 90% CI for the ratio will be provided.

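### Does SAP Table 8-3 need to say whether CLcr controls are pooled, and add a comparison with each group's own matched controls?

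*SAP*

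**What the plan says.** SAP Table 8-3 lists mild, moderate and severe impairment by CLcr, each against the same reference, "Normal CLcr ≥ 90 mL/min". SAP 8.2.2 adds that "All subjects with available data for the PK parameter under evaluation will be included in the modeling" and that "The statistical model will include renal function group as a fixed effect". SAP 3.2 states "No covariates will be included in analyses".

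The matching is described elsewhere. The objective (SAP 1.1) and the synopsis statistical methods refer to matched controls. Protocol 4.1 matches on age (±10 years), gender and BMI (±20%). Under SAP 1.3 a control can serve several cohorts but only one impaired subject within a cohort. Cohort 2 recruits new controls only "if none of the healthy subjects from a previous cohort is an appropriate match for a severe impairment subject", with parallel wording for Cohort 3. SAP 4.1 uses the match information for a listing. SAP 2.4 declares "No changes from protocol-specified analyses are planned".

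Pooling across cohorts is spelled out once, for the other categorization: "Subjects from all cohorts will be pooled and regrouped according to their MDRD-based eGFR values as follows" (SAP 8.2.1).

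**The concern.** The study matches individuals and sizes each cohort at 8 v 8, yet the model contains no cohort, pair or covariate term. If Cohort 2 or 3 opens and recruits new controls, the pooled reading puts people recruited for other impaired subjects into each row's reference. They may differ in age, sex or BMI from the group they are compared with, and nothing adjusts for that. The moderate group's reference could also be larger in the final report than when the sponsor decided whether to open further cohorts.

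The text seems to leave room for a second reading. Pooling is explicit only for eGFR, and the sample code has a two-group contrast, "estimate 'Impaired versus Normal' treat 1 -1 / cl alpha = 0.10", which would fit a separate dataset per row. Two programmers might then build different references for the primary endpoints, and one of the resulting ratios might not be the matched-control ratio named in the synopsis.

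**Working it through.** **1. What the text defines**

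- SAP 1.3 classes any subject with rounded CLcr of at least 90 mL/min as normal, with no reference to cohort or match. Table 8-3 uses that category in all three rows, and SAP 8.2.2 admits every subject with data.
- Protocol 8.7 names one control group. The synopsis lists one normal group beside the three impaired ones. Protocol 4.1 describes the control group as a whole as matched, so pooled controls still fit the synopsis wording.
- Where the SAP wants a split by cohort, it asks for one: the disposition summary in SAP 4.1 does so, and 8.2.2 does not.
- The eGFR set needs an explicit pooling sentence because subjects are moved out of their CLcr groups. That does not imply that CLcr controls are kept apart.
- The sample code does not settle the matter. Its contrast names `treat`, which is in neither the CLASS nor the MODEL statement, a clerical slip. With group as the only effect and a separate variance per group, a two-group fit and a four-group fit give the same difference and standard error.

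**2. The plan's own figure**

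Inputs from Protocol 8.8 and SAP 1.4: 8 v 8, log-scale SD 0.35, true ratio 1.0, limits 50% to 200%, 0.05 per side. The probability is P(|d| + t(0.95, 14) × s × √(1/8 + 1/8) < ln 2), integrated over the distribution of s. The result is 96.6%, which agrees with the stated value of over 95%. With equal variances and no reuse of controls, the same calculation gives 99.5% for 8 v 16 and 99.8% for 8 v 24.

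**3. Accuracy of the pooled reference**

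Assumption, not in the documents: added controls differ from a group's own matched controls by a log shift δ of 0 to 0.15.

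- SE = 0.35 × √(1/n1 + 1/n2)
- Bias = share of added controls × δ
- RMSE = √(SE² + bias²)
- Break-even δ = √(0.175² − SE²) / share

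| Design | Added share | SE | RMSE, δ = 0 to 0.15 | Bias in ratio at δ = 0.15 | Break-even δ |
|---|---|---|---|---|---|
| 8 v 8, own matched | 0 | 0.175 | 0.175 | none | – |
| 8 v 12 | 1/3 | 0.160 | 0.160–0.167 | 5.1% | 0.214 |
| 8 v 16 | 1/2 | 0.152 | 0.152–0.169 | 7.8% | 0.175 |
| 8 v 24 | 2/3 | 0.143 | 0.143–0.174 | 10.5% | 0.152 |

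Worked line for 8 v 24 at δ = 0.15: SE = 0.35 × √(1/8 + 1/24) = 0.1429; bias = 2/3 × 0.15 = 0.10; RMSE = √(0.0204 + 0.0100) = 0.1744; exp(0.10) = 1.105.

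The break-even shifts correspond to added controls with exposure about 24%, 19% and 16% higher, or 19%, 16% and 14% lower.

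**4. Interval width and coverage**

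With separate group variances and an estimated ratio of 1.0, the 90% intervals are:

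- 8 v 8: 0.735–1.361
- 8 v 12: 0.756–1.323
- 8 v 16: 0.766–1.306
- 8 v 24: 0.775–1.290

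In simulation (200,000 runs), coverage of the matched ratio is 90.3% for 8 v 8. At δ = 0.15 it is 89.0%, 86.5% and 82.7% for the three pooled designs. The chance that the interval lies within 50% to 200% stays at about 98% or more in every pooled case.

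**The case for a change.** The strongest argument for a change is that matching defines the comparison. New controls are recruited because existing ones failed to match, so they may well be unlike the other cohorts' impaired subjects. Cockcroft-Gault clearance contains age and weight, so age and body size may differ between CLcr groups. The study is open-label and the sponsor reviews PK data before opening cohorts, so an unstated reference could be settled after results are seen. The match data will exist anyway, and own-matched ratios would add at most 3 parameters × 3 rows = 9 figures.

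Parts of this stand. No sentence states pooling for the CLcr set, and a large enough shift would make the pooled ratio the less accurate one. If added controls had 1.5 times the exposure, the estimated ratio would be multiplied by 0.82 with two equal cohorts or 0.76 with three.

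What does not follow is that the plan should change. Nothing in the documents supports a shift of that size, or of any size. The 2/3 share needs both adaptive cohorts and no reuse of controls. Cohort 3 opens only after a change of at least twofold in Cohort 1, whereas Protocol 1.5 expects a limited renal effect. Own-matched ratios would give up precision to remove a bias that cannot be sized, and would put a second, possibly conflicting ratio in each row. Adjusting for three covariates with about 8 impaired subjects has no demonstrated gain.

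**Conclusion.** The plan can stand. The missing statement is a gap that an analyst fills sensibly from the surrounding text: one normal group, all controls with data, the same reference in every row. The choice behind it is a fair trade-off. Over the assumed shift range of 0 to 0.15, pooling has the lower RMSE throughout, though only just at the extreme (0.174 against 0.175), and there coverage drops to 82.7%. Beyond a log shift of 0.152 to 0.214, depending on the share of added controls, own-matched controls would be more accurate.

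These results rest on an SD of 0.35, 8 evaluable impaired subjects per group and the assumed shift. If only Cohort 1 is enrolled, if all controls are reused, or if added controls have the same exposure, there is no bias. The sample-size statement and the Cohort 3 trigger are unaffected in any case. A sentence in SAP 8.2.2 naming the pooled reference would be harmless, but the analysis does not depend on it.

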Height: Screening

Weight: Screening, Day -1

Clinical laboratory tests (blood chemistry, and urinalysis): Screening, Days -1, 1 (4 hours postdose), 2, 3, 6, and at the follow-up visit 14 (\pm 1) days after last dose or at the ET visit, if applicable

Clinical laboratory tests (hematology and coagulation): Screening, Days -1, 1 (4 hours postdose), 3, 6, and at the follow-up visit 14 (\pm 1) days after last dose or at the ET visit, if applicable.

Urine Drug and Alcohol Assessments: Screening, Day -1

12-lead ECG: Screening, Days -1, 1 (postdose), 6, and at the follow-up visit 14 (\pm 1) days after last dose or at the ET visit, if applicable

Serum Pregnancy Test (women of childbearing potential only): Screening, Day -1, 6, and at the follow-up visit 14 (\pm 1) days after last dose or at the ET visit, if applicable

Serology Test (HBV, HCV, HIV): Screening

Assessment of adverse events and concomitant medications will continue throughout the study.

Test Product, Dose, and Mode of Administration:

GS-9876 2 × 10 mg tablet, oral, administered fasted

Criteria for Evaluation:

Safety: Safety will be assessed during the study through the reporting of AEs, and by clinical laboratory tests, physical examinations, vital signs, and ECGs at various time points during the study. Concomitant medication usage will be assessed throughout the study.

Efficacy: Not applicable.

Pharmacokinetics: The following plasma PK parameters will be calculated, as appropriate: C_{max} , T_{max} , C_{last} , T_{last} , λ_z , AUC_{last} , AUC_{0-24} , AUC_{inf} , $\%AUC_{exp}$, $t_{1/2}$, CL/F , and V_z/F .

PK of predominant GS-9876 metabolites (if applicable) may be explored. In addition, urine parameters (e.g. renal clearance and percentage of dose excreted in urine) may be estimated.

Statistical Methods:

Pharmacokinetics:

Pharmacokinetic parameters for GS-9876 will be listed and summarized by renal function group (normal, mild, moderate, and severe impairment) using descriptive statistics.

An analysis of variance appropriate for a parallel design will be fit to the natural logarithm-transformed PK parameters (AUC_{last} , AUC_{inf} , and C_{max}) for GS-9876. Two-sided 90% confidence intervals (CIs) will be constructed for the geometric least-squares means (GLSM) ratio of PK parameters for GS-9876 in groups of subjects with renal impairment versus matched controls.

Safety:

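### The 1 -1 contrast behind the primary ratios relies on a renal-group level order that SAP 8.2.2 never fixes; it gives impaired over normal only in a two-group run with Normal sorted last

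*SAP*

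**What the plan says.** The code in SAP 8.2.2 declares "class renalgrp subjid" and fits "model lnest = renalgrp / ddfm=kr". It then requests "lsmeans renalgrp / e diff cl alpha = 0.1" and one contrast, "estimate 'Impaired versus Normal' treat 1 -1 / cl alpha = 0.10". Saved output is set by "ods output Estimates = LS_Diffs LSMeans = LS_Means CovParms = MSE", so the data set called LS_Diffs holds the ESTIMATE result, and the LSMEANS differences table is not kept.

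The text after the code makes ESTIMATE the source of the point estimate and interval, and continues: "The test-to-reference ratio (GLSM ratio) and associated 90% CI will be calculated by taking the exponential of the point estimate". The required direction is therefore test over reference.

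Table 8-3 lists seven comparisons, each against Normal: mild, moderate and severe by CLcr, and those three plus end stage by eGFR. One test label is "Severe Impairment CLcr 15-29 mL/min". Each row covers three parameters.

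**The concern.** The coefficients 1 and -1 attach to the first and second levels of the class variable in sorted order. Nothing in the SAP says what that order is. As printed, the statement names an effect (`treat`) that is in neither CLASS nor MODEL, so it should be rejected. The natural repair is to write renalgrp. The statement then runs, and the label 'Impaired versus Normal' is printed whichever groups are being contrasted and in whichever direction.

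At stake is the direction of the exposure change, which is the study's primary question. A rise in exposure in severe impairment could be reported as a fall.

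**Working it through.** **Inputs.** Contrast, CLASS, MODEL and ODS lines: SAP 8.2.2. Group labels: Table 8-3. Eight evaluable subjects per group, log-scale SD 0.35, 90% CI, limits (50%, 200%): SAP 1.4. SAS behaviour is assumed from general knowledge and was not run: levels sort by formatted value when no order is given, omitted coefficients are zero, and an effect absent from the model is rejected.

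**1. The plan's own figure.** Exact two one-sided tests: the probability that the estimate d satisfies -ln 2 + h < d < ln 2 - h, where h = t(0.95, 14 df) × s × √(2/8), d is normal with mean 0 and SD 0.35 × √(2/8), and the result is averaged over the chi-square distribution of s². Result: 96.6%. The stated figure of over 95% reproduces, and the sample size is not affected by this point.

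**2. What 1 -1 estimates if the Table 8-3 labels are the class values** (after `treat` becomes renalgrp):

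| Groups in the run | Sorted order | 1 -1 estimates | Wanted? |
|---|---|---|---|
| Mild, Normal | Mild, Normal | Mild − Normal | yes |
| Moderate, Normal | Moderate, Normal | Moderate − Normal | yes |
| End Stage, Normal | End Stage, Normal | End Stage − Normal | yes |
| Severe, Normal | Normal, Severe | Normal − Severe | inverted |
| CLcr, three groups | Moderate, Normal, Severe | Moderate − Normal | one row only |
| CLcr, four groups | Mild, Moderate, Normal, Severe | Mild − Moderate | no row |
| eGFR, five groups | End Stage, Mild, Moderate, Normal, Severe | End Stage − Mild | no row |

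**3. Other codings, pairwise CLcr runs.** Codes running from 0 = Normal to 3 = Severe invert every comparison. Codes running from 1 = Severe to 4 = Normal invert none.

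**4. Pairwise or pooled?** SAP 8.2.2 supports either reading. It puts all subjects with data for the parameter into the modelling, which suggests a pooled fit. It also sets a minimum of 3 subjects in both the test and the reference group, and the contrast has two coefficients, which suggests pairwise fits.

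**5. Size.** h = 1.761 × 0.35 × √(2/8) = 0.308, and exp(0.308) = 1.361. With equal group sizes and equal sample SDs, the SAP's separate-variance model has the same standard error.

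- Ratio 2.00: 2.00/1.361 = 1.47 and 2.00 × 1.361 = 2.72. Inverted: 1/2.00 = 0.50, with limits 1/2.72 = 0.37 and 1/1.47 = 0.68.
- Ratio 1.50 (1.10 to 2.04). Inverted: 0.67 (0.49 to 0.91).

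**6. Would the equivalence limits expose it?** No. An inverted interval is the exact reciprocal, and (50%, 200%) is symmetric on the log scale, so an interval lies inside the limits exactly when its reciprocal does.

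**The case against.** The strongest reply is that the intended direction is not in doubt. Table 8-3 names test and reference in every row, the text asks for test over reference, and a two-group template with Normal last gives exactly that. The printed code cannot silently return a wrong number, because the misnamed effect stops it, and that line must be rewritten anyway. The code also saves the group least-squares means, and SAP 8.2.1 asks for geometric means by renal function group. A reported 0.50 would then sit beside a severe mean twice the normal mean. All of this stands. It makes a reversal detectable, but it does not make the specified code correct.

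Three stronger readings are tempting, and the documents do not support them.

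- *The severe ratio will be inverted.* This needs the Table 8-3 headings to be the sorted values of renalgrp, and neither document says so.
- *Every ratio will be inverted because the protocol lists normal first.* The Synopsis text, "summarized by renal function group (normal, mild, moderate, and severe impairment) using descriptive statistics", is prose about descriptive summaries and says nothing about class levels.
- *No single run can give the listed comparisons.* Within one categorization, the LSMEANS line already prints every pairwise difference with a 90% CI. The limit applies to the single ESTIMATE that the SAP reports from. The two categorizations need separate runs in any case.

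**Conclusion.** The point holds in conditional form. The stated code for the primary endpoints gives the specified ratio only for a two-group run with Normal sorted last, and the SAP secures neither condition. This is more than missing detail, because the contrast can return a reversed or unrelated comparison under the 'Impaired versus Normal' label.

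The extent depends on coding and enrolment. With the Table 8-3 labels and pairwise runs, at most 2 of 7 rows (severe by CLcr and by eGFR), or 2 × 3 = 6 of 21 ratios, would be inverted. That maximum assumes every group exists with at least 3 subjects. Cohorts 2 and 3 may never be enrolled; with Cohort 1 alone, the CLcr comparison is correct under those labels.

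A final CLcr data set of moderate, severe and normal is plausible, since Cohort 3 opens only after a change of at least 2-fold in Cohort 1 and Protocol 1.5 expects a limited effect. In that case, under those labels, neither route gives the correct Severe/Normal ratio from this statement: the pairwise run inverts it and the pooled run omits it. The LSMEANS differences are printed, but they are neither saved nor named as the reporting source, and with those labels they too would show Normal minus Severe.

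**What to change.** Make these changes in SAP 8.2.2 together with the correction of `treat`:

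1. Define the values of renalgrp, with 'Normal' as the reference, and state whether models are fitted pairwise or to all groups within a categorization.
2. Use `lsmeans renalgrp / diff=control('Normal') cl alpha=0.1`, with the string matching the stored label exactly. Each difference is then impaired minus Normal, whatever the sort order or number of groups.
3. Save the Diffs table in the ODS line, and amend the paragraph after the code to name it as the source of the ratios and 90% CIs.

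Alternatively, fix the level order and write one ESTIMATE per Table 8-3 row with full coefficients. With the order Mild, Moderate, Severe, Normal, the severe row is 0 0 1 -1. Coefficients must be adapted if a group is absent.

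The cost is two lines of code, a definition of renalgrp and a sentence of text. No new data are needed. The model already has a separate mean and variance for each group, so the intended estimates do not change.

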## PHARMACOKINETIC ABBREVIATIONS AND DEFINITIONS

$AUC_{last}$	area under the plasma/serum concentration versus time curve from time zero to the last quantifiable concentration
$AUC_{inf}$	area under the plasma/serum concentration versus time curve extrapolated to infinite time, calculated as $AUC_{last} + (C_{last}/\lambda_z)$
$\%AUC_{exp}$	percentage of AUC extrapolated between $AUC_{last}$ and $AUC_{inf}$
$C_{max}$	maximum observed plasma/serum concentration of drug
$C_{last}$	last observed quantifiable plasma/serum concentration of the drug
$CL/F$	apparent oral clearance after administration of the drug: $CL/F = Dose/AUC_{inf}$ , where “Dose” is the dose of the drug
$\lambda_z$	terminal elimination rate constant, estimated by linear regression of the terminal elimination phase of the log plasma/serum concentration of drug versus time curve of the drug
$T_{max}$	time (observed time point) of $C_{max}$
$T_{last}$	time (observed time point) of $C_{last}$
$t_{1/2}$	estimate of the terminal elimination half-life of the drug in plasma/serum, calculated by dividing the natural log of 2 by the terminal elimination rate constant ( $\lambda_z$ )
$V_z/F$	apparent volume of distribution of the drug
$A_e$	Amount of unchanged drug excreted in urine calculated either over a specific interval ( $A_{e(interval)}$ ) or cumulatively over all collection intervals, calculated as (Concentration of unchanged drug in urine) · (Volume of urine collected)
$CL_r$	The renal clearance of unchanged drug in a specific interval ( $CL_{r(interval)}$ ) or cumulatively over all collection intervals
$\% Dose_{excreted}$	The percentage of given dose excreted in the urine as unchanged drug

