#### **1.4. Sample Size and Power**

With 16 (8 per group) evaluable subjects, the estimated two-sided 90% CI of the GLSM ratio of test versus reference groups, with regards to PK parameters (AUC and  $C_{\max}$ ) would be within (50%, 200%) with over 95% probability. This calculation is based on a two group t-test of equivalence in means at the significance level of 0.05, assuming the expected geometric means ratio of 1.0 and inter-subject standard deviation (SD) of no more than 0.35 on a natural logarithm scale. The assumption about the inter-subject SD is supported by previous Gilead study GS-US-379-1372 using the maximum variability for AUC and  $C_{\max}$  from the closest dose levels (15 mg and 30 mg) of the dose in this study. An overage of 2 subjects per group will be enrolled to accommodate subject drop-outs, thus requiring a total enrollment of 20 subjects (10 per group) for each cohort.

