### **3.4. Multiple Comparisons**

All endpoint tests will be done at the significance level of 0.05 with no multiplicity adjustments.

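### For t1/2 and Vz/F the SAP plans no between-group ratio or interval, only an optional Wilcoxon p-value that cannot bound a moderate change at 8 per group

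*SAP*

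**What the plan says.** SAP Section 8.2.2 fits an ANOVA to the log-transformed parameters and promises "The ratio of geometric least squares means (GLSMs) for the PK parameter in comparison between the test and reference groups and the 90% CI". Table 8-3 limits these comparisons to AUCinf, AUClast and Cmax.

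For CL/F, Vz/F and t1/2, the text after Table 8-3 says that nonparametric analyses are routine and then that, when needed, "these analyses can be performed using the Wilcoxon rank sum test for parallel design between the test and reference groups". The code calls PROC NPAR1WAY with the `wilcoxon` option alone.

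SAP Section 3.4 adds: "All endpoint tests will be done at the significance level of 0.05 with no multiplicity adjustments".

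SAP Section 8.1.1 and Table 8-1 list t1/2, CL/F and Vz/F among the parameters used to evaluate the PK objectives. SAP Section 8.2.1 plans, within each renal function group, the geometric mean, a 95% CI, and the mean and SD of the log values.

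**The concern.** The primary objective is a comparison with matched controls, and the sample size rests on bounding that comparison: the 90% CI should lie within 50% to 200%. For t1/2 and Vz/F the only between-group method named is a test of no difference. Its p-value gives neither the size of a change nor the range of changes that the data leave open.

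Half-life and volume help to show whether an exposure change comes from slower elimination or from altered distribution or absorption. Half-life also bears on the claim in Protocol Section 1.3 that a single dose predicts steady-state PK. A bare non-significant result in the report could be taken as no effect on half-life when a moderate change has not been excluded. If the optional test is not run, these parameters get no between-group inference at all, and the SAP does not say what would make the test needed.

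**Working it through.** **Inputs**
- SAP 1.4: "With 16 (8 per group) evaluable subjects", "inter-subject standard deviation (SD) of no more than 0.35 on a natural logarithm scale" (stated for AUC and Cmax), and "assuming the expected geometric means ratio of 1.0".
- SAP 1.3: enrolment is "10 per group, moderate renal impairment and matched healthy controls", so up to 10 per group.
- Test level 0.05 (SAP 3.4), assumed to apply here and assumed two-sided.
- SD of ln(t1/2) and ln(Vz/F): not in the documents. Assumed 0.35, with a range of 0.25 to 0.50.

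**1. The plan's own figure.** On the ln scale the SE is 0.35 × √(2/8) = 0.175 and t(0.95, 14) = 1.761, so the 90% CI half-width is 1.761 × 0.175 = 0.308. The CI lies within 50% to 200% when the estimated difference is within ln 2 − 0.308 = 0.385 of zero. With the SD held at 0.35 that is 0.385/0.175 = 2.20 SEs, a probability of about 97%. Integrating over the sampling distribution of the SD gives 96.6%. The stated figure of over 95% reproduces.

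**2. Miss rate of the Wilcoxon test.** Log-normal data were simulated, 200,000 trials per scenario, with W the rank sum of the impaired group. The exact test at 8 v 8 rejects when W ≤ 49 or W ≥ 87. The normal approximation uses z = (|W − 68| − 0.5)/√(8 × 8 × 17/12). Proportion of trials not significant (exact / approximation):

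| True change | SD 0.25 | SD 0.35 | SD 0.50 |
|---|---|---|---|
| 1.25-fold | 63% / 68% | 79% / 82% | 87% / 90% |
| 1.5-fold | 17% / 20% | 45% / 50% | 69% / 73% |
| 2-fold | <1% / <1% | 5% / 7% | 29% / 34% |

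With 10 per group and SD 0.35 the misses are 76%, 36% and 2%. With 8 impaired subjects against 16 pooled controls, a 1.5-fold change is missed in 32% instead of 50% (approximation).

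**3. What a non-significant result leaves open.** At a true 1.5-fold change, SD 0.35 and 8 per group, the 90% CI of the ratio still reaches beyond 2 in about 28% of the non-significant trials (approximation; unequal-variance interval).

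**4. What an interval would show.** At 8 per group and SD 0.35 the expected 90% CI is the estimate divided and multiplied by exp(0.308) = 1.36:
- an estimate of 1.25 gives 0.92 to 1.70;
- 1.5 gives 1.10 to 2.04;
- 2.0 gives 1.47 to 2.72.

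The factor is 1.25 at SD 0.25 and 1.55 at SD 0.50.

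**5. CL/F.** The SAP defines "apparent oral clearance after administration of the drug" as Dose/AUCinf, and every subject receives 20 mg (Protocol 5.3). So ln(CL/F) = ln(20 mg) − ln(AUCinf), and the CL/F ratio and its CI are exactly the reciprocals of those for AUCinf.

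**6. Smallest groups.** SAP 8.2.2 allows comparisons with 3 subjects per group. If that also governs the Wilcoxon test, there are C(6,3) = 20 rank arrangements at 3 v 3. The smallest exact two-sided p is 2/20 = 0.10, so significance at 0.05 is impossible.

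**The case against.** The primary endpoints are AUClast, AUCinf and Cmax and the secondary endpoints are safety. Protocol Section 8.7 promises ratios only for the three exposure measures, so nothing promised is missing. The within-group log means and SDs in SAP 8.2.1 let a reader derive a ratio and an unpaired interval. The test is worded as optional, and no rule equates non-significance with no effect. All of this stands and keeps the point minor. It does not explain why the SAP leaves the between-group estimate to the reader when it has already written the model that would give it.

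Three stronger readings are tempting, and the documents do not support them.

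- *CL/F also lacks an estimate and interval.* It does not: the planned AUCinf ratio and CI, inverted, supply both. Only a redundant test remains.
- *A relevant change would usually come out as not significant.* The only change the documents call substantial is 2-fold or more, for exposure (SAP 1.3), and at SD 0.35 that is missed in only 5 to 7% of trials. At 1.5-fold the chance is about even. No relevant change is defined for t1/2 or Vz/F.
- *The CL/F test can contradict the primary result.* At a true 1.5-fold change, about 21% of trials have a non-significant Wilcoxon test on CL/F beside an AUCinf 90% CI that excludes 1. Most of this comes from setting a 0.05 test against a 90% CI: with both methods at 0.05 it falls to about 8%. The 90% CI is also planned as a bound in the two one-sided tests framework, not as a test of a ratio of 1.

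**Conclusion.** The point holds for t1/2 and Vz/F, as a cheap improvement of minor severity. The SAP plans no between-group ratio or interval for them, and the one method it names cannot bound a moderate change at the planned size. The miss rates assume log-normal data, equal SDs in the two groups and, for the headline figures, 8 per group with an SD of 0.35 borrowed from AUC and Cmax. They worsen at an SD of 0.50, improve at 0.25, and improve if controls are pooled across cohorts. The absence of a planned interval depends on none of these assumptions. No primary analysis or cohort-enrolment decision is affected.

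**What to change.** In SAP Section 8.2.2:

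1. Add ln(t1/2) and ln(Vz/F) to the PROC MIXED analysis already specified (group-specific variances, Kenward-Roger degrees of freedom) and report the GLSM ratio with its 90% CI. When the code is reused, note that its ESTIMATE statement names `treat`, while the CLASS and MODEL statements name `renalgrp`; the two must agree.
2. If a rank method is kept for these two parameters, apply it to log values and request the Hodges-Lehmann shift with a 90% CI (`hl alpha=0.1`), then exponentiate. State when it will be run and that non-significance is not read as absence of effect.
3. Report CL/F as the reciprocal of the AUCinf ratio and CI, and drop its Wilcoxon test.

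The cost is a few lines of text and code, with no new data or subjects. The downside is two more model-based intervals per comparison, which rely on log-normality.
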